10.2 Sample Size Considerations

The proposed sample sizes are 33 per group for a total of 66 subjects in 2 treatment groups (one AQ-13 group receiving 1596 mg orally + one Coartem control group) for this Proof of Concept Study of AQ-13 in adult Malian males \geq 18 years of age with uncomplicated malaria (Flow Charts 2-3 on pages 16-17 and Flow Chart 4 on page 26).

Because sample sizes vary markedly with the efficacy of the comparator, accurate estimation of the Coartem cure rate is a key issue. The sample sizes estimated were based on an expected efficacy (cure rate) of 95% for Coartem [20-22, 25-27] and a conservative 20% estimate of attrition after treatment. An expected cure rate of 95% has been used for Coartem because this estimate is at the lower end of the range of cure rates reported in the recent literature (93.9%, 95.5%, 97.1%, and 97.5%) [20-22, 36], and because it simultaneously recognizes recent concerns about *in vivo* selection by Coartem for the 86N allele of *pfmdr1* in *P. falciparum*, which has the potential to further reduce the cure rate [37-38].

Another major factor is the width of the non-inferiority margin (M), the range within which the investigational drug is considered non-inferior to the comparator (control). We have used a value of $M = 15\%$. In the recent Guidance Document “Non Inferiority Clinical Trials” [Mar 2010], M equal to 40% of the efficacy of the positive control is stated to be a statistically persuasive result for phase III trials of drugs in general and elsewhere in this document it is stated that a non-inferiority margin of 50% for cardiovascular drugs is equivalent to a non-inferiority margin of 10-15% for antibiotics. From these statements, we infer that for a candidate antimalarial such as AQ-13, a non-inferiority margin of 10-15% would be statistically persuasive for a phase 3 trial, in which case this margin should also be sufficient for the present Phase 2 Proof of Concept Efficacy Trial of AQ-13.

With $M=15\%$, a Coartem efficacy assumed to be 95% and a dropout rate up to 20%, a table from Machin and Campbell [Statistical tables for the design of clinical trials. Blackwell, Oxford: 1987, pp. 35-53] gives 33 patients per group as a sample size [80% power] (an excerpt from that table is provided as Table 8).

Table 8.
Effects of the Margin and the Dropout Rate on Sample Sizes
necessary to test for Non-Inferiority of AQ-13 to Coartem

Non-Inferiority Margin	Dropout Rate (percent)		
	0%	10%	20%
5%	235	261	294
7.5%	104	116	130
9%	73	81	91
10%	59	66	74
15%	26	29	33
20%	15	17	19

Although the sample size calculation was based on the primary endpoint of cure for all patients, based on studies we have performed in Mali previously, we expect that approximately 65% of the 26 evaluable subjects in each group will have CQ-resistant *P. falciparum* [35]. Therefore, subgroup analysis according to chloroquine susceptibility should make it possible to generate hypotheses about the efficacy of AQ-13, compared to Coartem, for subjects with either CQ-resistant or –susceptible parasites.

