Safety Oversight will be assisted by a Data Safety and Monitoring Board (see section 8.7 on page 33, below).

Flow Chart 2

PROOF OF CONCEPT STUDY FOR AQ-13 ADULT MALES WITH UNCOMPLICATED *P. falciparum* MALARIA

Recruitment in the Villages of Missira and Sirakoroba in Northwestern Mali
and from Outpatient Referral Clinics in the city of Bamako;

In-Patient Studies at the Clinical Research Center, Hôpital Point G in Bamako

Flow Chart 3**PROOF OF CONCEPT STUDY FOR AQ-13
RANDOMIZATION, DRUG ADMINISTRATION AND FOLLOW-UP**

Recruitment in the Villages of Missira and Sirakoroba in Northwestern Mali

and from Outpatient Referral Clinics in the city of Bamako;

In-Patient Studies at the Clinical Research Center, Hôpital Point G in Bamako

EYE EXAMS, HOLTER RECORDINGS, CHEMISTRY PANEL, HEMATOLOGY (CBC)
(n=70; 35 each for the AQ-13 and Coartem groups, expected 5% ineligible).

•INCLUSION CRITERIA:

≥ 2,000 asexual *P. falciparum* parasites per μ l,
Uncomplicated *P. falciparum* malaria,

•Baseline Screening Holter Recording x 1 hour,**•Visual Screening** baseline acuity, visual fields,**•EXCLUSIONS:** Hb ≤ 7 gms/dL, K+ ≤ 3.5 mEq/L, arrhythmias, heart block, BP ≥ 140/90 or severe or complicated malaria.

RANDOMIZE ELIGIBLE ADULT VOLUNTEERS WITH UNCOMPLICATED *P. falciparum* MALARIA
(n=66; 33 each for the AQ-13 and Coartem groups, expected 20% loss to follow-up).

•Filter Paper Blots for molecular studies,**•Freeze Initial Parasites** at -70° C,**•pfcr PCR and other Tests** for CQ Resistance,**•Oral Administration of 700 mg AQ-13 on days 1-2,** followed by 350 mg on day 3, OR

Oral Administration of Coartem, 80 mg artemether

+ 480 mg lumefantrine twice daily x 3 days,

•Repeat Daily Blood Smears (days 1 through 7), repeat Hematology, Chemistry panels on day 4,**•AQ Drug and Metabolite Levels** at 0, 0.5, 1, 2, 4, 6, 12, 18, 24, 24.5, 25, 26, 28, 30, 36, 48, 48.5, 49, 50, 52, 54, 60, 72, 96 and 120 hours x 5 ml,**•Holter Monitoring** 24 hours/day x 4 inpatient days,**•One Week** eye exam, 1 hour Holter recording,**•WITHDRAWAL:** severe or complicated malaria.

FOLLOW-UP
for a total of 6 weeks,
PRIMARY ENDPOINT is
a lack of recrudescence
with the same genotype(s)
(n=28 evaluable subjects/group)

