10.3 Analysis Plan

This is a Proof of Concept Efficacy Study of AQ-13 in comparison to the gold standard (Coartem). Thus, this study in adult Malian males can be viewed as a non-inferiority study, comparing one dose of AQ-13 (1596 mg orally over 3 days) to Coartem [39].

The null and alternative hypotheses to be tested are:

$$H_0 = (C - E) \geq M \quad (\text{control is superior to experimental})$$

$$H_1 = (C - E) < M \quad (\text{experimental is not inferior to control})$$

C is the efficacy of the comparator (Coartem), E the efficacy of the investigational drug (AQ-13) and M the non-inferiority margin. $M = 15\%$ will be used (see above). AQ-13 will be considered equivalent to (not inferior to) the comparator (Coartem) if the null hypothesis is rejected with a one-sided alpha of 0.025 [29, 40]. Cure rates, adjusted for reinfection, will be calculated for AQ-13 and Coartem and differences between cure rates with AQ-13 and Coartem will be calculated with 95% confidence intervals. Non-inferiority of AQ-13 will be established if the upper limit of the 95% CI for the difference between AQ-13 and Coartem is less than the non-inferiority margin of 15% [28-29].

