Analyses will be performed based on both the original randomization (intent-to-treat, ITT) and the subset of patients who complete the study protocol, for whom complete information is available (per-protocol analysis). Paradoxically, intent-to-treat (ITT) analysis poses a special problem in non-inferiority trials. ITT is in fact a non-conservative approach in non-inferiority trials because the inclusion of non-compliant subjects and dropouts dilutes the differences between treatments and therefore, favors the conclusion that the drugs are equivalent [39]. However, we expect the differences between ITT and per-protocol analyses will be small because drug administration under direct observation should reduce noncompliance to very low levels. Nevertheless, every effort will be made to obtain follow-up data on non-compliant subjects and subjects who drop out because of adverse events (AEs). In contrast, excluding subjects with protocol “violations” (per-protocol analysis) can bias the analysis toward concluding equivalence of the two drugs. This would be the case if drop outs from the investigational treatment were related to non-response (treatment failure). Thus, excluding those dropouts from the per-protocol analysis could inflate the efficacy estimate for the investigational drug and lead to an inappropriate conclusion of non-inferiority. Careful examination of the data from subjects who are excluded from the analysis helps to detect such bias and facilitates the correct interpretation of trial results.

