14.4 Timing of Reports

For this abbreviated Phase 2 Proof of Concept Efficacy Study, there will be two reports. The first report will be provided after 15 subjects have been enrolled in each of the two arms of the protocol (AQ-13 and Coartem) and have completed their follow-ups (Interim Analysis for Futility – section 8.6 of this protocol on page 32). The second report (Final Analysis for Efficacy, Adverse Events and Pharmacology) will be provided after 18 additional subjects have been enrolled in each arm (total of 66 subjects) and have completed their follow-ups.

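### The 80% power in 10.2 belongs to a one-sided 0.05 test; under the one-sided 0.025 rule in 10.3 the same formula gives about 70% at 26 evaluable per arm

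*Combined protocol and SAP*

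**What the plan says.** Section 10.2 assumes a Coartem cure rate of 95%, a margin of 15 percentage points and "a conservative 20% estimate of attrition after treatment". From a published table, excerpted as Table 8, it "gives 33 patients per group as a sample size [80% power"]. The zero-dropout entry for a 15% margin is 26 per arm, and the 20% dropout entry is 33. Neither the text nor the table gives an alpha or says whether the test is one- or two-sided.

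Section 10.3 does give the alpha. AQ-13 is declared non-inferior "if the null hypothesis is rejected with a one-sided alpha of 0.025". The operational version is "Non-inferiority of AQ-13 will be established if the upper limit of the 95% CI" for the difference in cure rates lies below 15%. The method for that interval is not named. On the analysis sets, 10.3 says: "Analyses will be performed based on both the original randomization (intent-to-treat, ITT) and the subset of patients who complete the study protocol". It gives no rule for missing outcomes.

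The evaluable number varies. Below Table 8, 10.2 says "we expect that approximately 65% of the 26 evaluable subjects in each group will have CQ-resistant" parasites. Flow Chart 3 in section 4 randomises "n=66; 33 each for the AQ-13 and Coartem groups, expected 20% loss to follow-up", and section 14.4 places the final report "after 18 additional subjects have been enrolled in each arm (total of 66 subjects"). Yet Flow Chart 3 and section 5.1 give 28 evaluable per arm.

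**The concern.** A power figure means something only for the test that will be run. Section 10.2 prints 80% without an alpha, so a reader will attach it to the only alpha in the plan, the one-sided 0.025 of 10.3. If Table 8 was built on a looser alpha, the power for the primary hypothesis is overstated, and a result that misses the margin would be read against a 20% miss rate that the design does not have.

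The unnamed interval matters too. With cure near 95% and fewer than 35 patients per arm, common intervals for a difference in proportions differ widely in both power and false-positive rate.

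**Working it through.** **Inputs.** Cure 95% for Coartem, margins and dropout rates as in Table 8, 80% power (10.2); one-sided 0.025, M = 15% (10.3). AQ-13 cure of 95% is an assumption: the plan expects similar efficacy and gives no number, but this value reproduces Table 8.

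**1. Reproducing Table 8 (zero dropout).** n per arm = 2 × 0.95 × 0.05 × (z_alpha + z_power)² / M².

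| Margin | Table 8 | One-sided 0.05 | One-sided 0.025 |
|---|---|---|---|
| 5% | 235 | 234.9 | 298.3 |
| 7.5% | 104 | 104.4 | 132.6 |
| 9% | 73 | 72.51 | 92.1 |
| 10% | 59 | 58.7 | 74.6 |
| 15% | 26 | 26.1 | 33.1 |
| 20% | 15 | 14.7 | 18.6 |

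For M = 15%: 0.095 × (1.645 + 0.842)² / 0.0225 = 26.1, and 26.1 / 0.8 = 32.6, hence 33. With 1.960 in place of 1.645 the result is 33.1 before dropout. At one-sided 0.05 every row rounds to the printed entry; at 0.025 none does. Alternatives at M = 15% (90% power, Farrington-Manning variance, continuity correction) give 36 to 51 per arm, not 26.

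**2. Power under the 10.3 rule, same formula.** Power = Φ(0.15 / √(2p(1−p)/n) − 1.960), with p = 0.95:

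- n = 26: Φ(2.482 − 1.960) = 69.9%. With 1.645 it is 79.9%, the printed figure.
- n = 28: Φ(2.575 − 1.960) = 73.1%.
- n = 33, no losses: Φ(2.796 − 1.960) = 79.8%.

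Across the Coartem cure rates cited in 10.2, applied to both arms, power at n = 26 runs from 62% (93.9%) to 93% (97.5%).

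**3. Exact power and error by interval.** Two binomials fully enumerated. The difference is Coartem minus AQ-13, as in the 10.3 hypotheses, and success is an upper 95% limit below 0.15. Power is at 95% in both arms; error is at 95% vs 80%. The maximum is over Coartem cure 90–100% with AQ-13 15 points lower.

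| n per arm | Interval | Power | Error | Maximum error |
|---|---|---|---|---|
| 26 | Plain Wald | 72% | 5.1% | 8.2% |
| 26 | Newcombe or score | 43% | 2.0% | 2.5% |
| 28 | Plain Wald | 70% | 4.0% | 6.3% |
| 28 | Newcombe or score | 55% | 2.1% | 2.3% |
| 33 | Plain Wald | 81% | 4.2% | 10.9% |
| 33 | Newcombe or score | 59% | 2.2% | 2.5% |

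The score interval is Miettinen-Nurminen. At n = 26 its power is 41% at 93.9% cure in both arms and 57% at 97.5%. Over the whole null boundary at n = 26 its error peaks at 2.7%.

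**4. Evaluable number.** 33 × 0.8 = 26.4, so 26. The figure 28 follows from 70 × 0.8 / 2, but 70 is the number consenting in section 5.1; 66 are randomised.

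**5. ITT.** No missing-outcome rule is given. If losses counted as failures (an assumption), cure would be 0.95 × 0.8 = 76% in both arms, and the formula at n = 33 gives about 30%.

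**The case against.** **All 33 may be evaluable.** Section 10.2 calls 20% conservative and treats it as an upper allowance; with no losses the formula gives 79.8%. That holds as arithmetic, but Flow Chart 3 expects a 20% loss and 10.2 itself works with 26. On the plan's own attrition the figure is 69.9%, and full follow-up does not reach 80% with Newcombe or score.

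**The 43% is one interval at one n.** This is fair. Exact power jumps with n: at 27, Newcombe gives 55.5% and score 42.8%. A continuity-corrected Wald interval at exactly 26 has 53.8% power and a maximum error of 2.52%. Agresti-Caffo gives 56% power at 26, with error up to 2.8% for Coartem cure of 90–100%. But the continuity-corrected interval's maximum error rises to 7.2% at 27 and 6.3% at 28, so its control depends on the final count landing on 26. None of these reaches 80%.

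**The evaluable number could be 28.** 28 of 33 is a loss of about 15%, within the allowance. The conflict still needs settling, and 73.1% is also short of 80%.

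**The ITT figure rests on an invented rule.** It does, so it is an illustration only.

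**This is a phase 2 proof of concept, and the success criterion itself is sound.** One-sided 0.025 and the upper limit of a two-sided 95% interval do agree. A proof-of-concept trial may accept lower power, but the plan should then state that power.

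**Conclusion.** The point stands. The 80% in 10.2 belongs to a one-sided 0.05 test, while 10.3 judges success at one-sided 0.025. On the plan's own formula and attrition, the chance of missing non-inferiority when both drugs cure 95% is about 30%, not 20%; with a Newcombe or score interval at 26 per arm it is about 57%. Plain Wald keeps power near 72% only by exceeding the 2.5% error that 10.3 sets.

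The alpha behind Table 8 is inferred, since 10.2 does not state it, but agreement in six rows of six makes the inference firm. The power figures assume 95% cure in both arms; a lower true AQ-13 cure rate would reduce them. The statement must be corrected, because it is the headline power for the primary hypothesis.

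**What to change.** 1. In 10.2, state that Table 8 corresponds to one-sided alpha 0.05 (normal approximation, 95% cure in both arms), and replace the 80% with the power under the 10.3 rule.
2. In 10.3, keep one-sided 0.025 and name one interval that holds the error at or near 2.5% over plausible cure rates and over the evaluable counts that could arise. The Miettinen-Nurminen score interval is one example. Plain Wald does not qualify; continuity-corrected Wald does so at 26 but not at 27 or 28.
3. Quote the exact power of the chosen interval at the evaluable number, with its range over the cited cure rates. For the score interval at 26 per arm that is 43% (41% at 93.9% cure, 57% at 97.5%). If 70% is shown, label it as a normal approximation conditional on 95% cure in both arms.
4. Use one evaluable number throughout. From 66 randomised with 20% loss it is 26 per arm, so the 28 in Flow Chart 3 and section 5.1 would change.
5. Say that the quoted power is for evaluable subjects. Give an ITT power only once a missing-outcome rule is written.

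The cost is protocol and SAP wording, and a clearly less favourable stated power. Keeping 80% would instead need 34 evaluable per arm by the formula (34 / 0.8 = 42.5, so 43 randomised) or 49 with the score interval (49 / 0.8 = 61.25, so 62 randomised). This point does not ask for that.

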10.3 Analysis Plan

This is a Proof of Concept Efficacy Study of AQ-13 in comparison to the gold standard (Coartem). Thus, this study in adult Malian males can be viewed as a non-inferiority study, comparing one dose of AQ-13 (1596 mg orally over 3 days) to Coartem [39].

The null and alternative hypotheses to be tested are:

$$H_0 = (C - E) \geq M \quad (\text{control is superior to experimental})$$

$$H_1 = (C - E) < M \quad (\text{experimental is not inferior to control})$$

C is the efficacy of the comparator (Coartem), E the efficacy of the investigational drug (AQ-13) and M the non-inferiority margin. $M = 15\%$ will be used (see above). AQ-13 will be considered equivalent to (not inferior to) the comparator (Coartem) if the null hypothesis is rejected with a one-sided alpha of 0.025 [29, 40]. Cure rates, adjusted for reinfection, will be calculated for AQ-13 and Coartem and differences between cure rates with AQ-13 and Coartem will be calculated with 95% confidence intervals. Non-inferiority of AQ-13 will be established if the upper limit of the 95% CI for the difference between AQ-13 and Coartem is less than the non-inferiority margin of 15% [28-29].

Analyses will be performed based on both the original randomization (intent-to-treat, ITT) and the subset of patients who complete the study protocol, for whom complete information is available (per-protocol analysis). Paradoxically, intent-to-treat (ITT) analysis poses a special problem in non-inferiority trials. ITT is in fact a non-conservative approach in non-inferiority trials because the inclusion of non-compliant subjects and dropouts dilutes the differences between treatments and therefore, favors the conclusion that the drugs are equivalent [39]. However, we expect the differences between ITT and per-protocol analyses will be small because drug administration under direct observation should reduce noncompliance to very low levels. Nevertheless, every effort will be made to obtain follow-up data on non-compliant subjects and subjects who drop out because of adverse events (AEs). In contrast, excluding subjects with protocol “violations” (per-protocol analysis) can bias the analysis toward concluding equivalence of the two drugs. This would be the case if drop outs from the investigational treatment were related to non-response (treatment failure). Thus, excluding those dropouts from the per-protocol analysis could inflate the efficacy estimate for the investigational drug and lead to an inappropriate conclusion of non-inferiority. Careful examination of the data from subjects who are excluded from the analysis helps to detect such bias and facilitates the correct interpretation of trial results.

Times to recrudescence and reinfection will be analyzed using life tables, and compared using the log rank test. Cox regression will be used to compare multiple (multivariate) predictors of times to recrudescence and reinfection. Pharmacokinetic parameters will be examined for AQ-13 doses and compared to data from the Phase 1 studies, as appropriate. **Using the same protocol as in the Phase 1 study [11], the relatedness of adverse events (AEs) to study drugs will be classified independently by two blinded physicians according to the definitions in section 8.3 on page 30 as unknown, not related, unlikely to be related, or possibly, probably or definitely related to the study drugs, based on temporal relationships and biological plausibility.** The frequencies of AEs will be compared between AQ-13 and Coartem using Pearson Chi-square. Because more than one AE may occur in an individual patient, the proportion of patients receiving AQ-13 with AEs will be compared with Coartem using Chi-square or the Fisher Exact test. The severity of AEs will be classified using the recent FDA Guidance for Healthy Adult and Adolescent Volunteers in Preventive Vaccine Trials [23], and the severity of AEs across the study arms will be compared using Chi-square. QT interval corrections for heart rate (QTc) will be made using both Bazett's and Fridericia's formulas [41-42]. Within-patient maximum changes from baseline will be assessed using the Wilcoxon test for paired observations. Between-group QT interval changes will be compared using ANOVA or Kruskal-Wallis.

HYPOTHESES BEING TESTED.

The primary hypothesis is that the efficacy of AQ-13 for uncomplicated *P. falciparum* malaria is similar to

that of Coartem - based on a non-inferiority margin of 15%. That is, that AQ-13 will produce a cure rate within 15% of the Coartem control (standard). The secondary hypothesis is that AQ-13 will have safety profiles in subjects with uncomplicated malaria comparable to those for AQ-13 in healthy volunteers [11].

EXPECTED OUTCOMES.

Our preliminary (previous) studies have shown that AQ-13 is:

- *active in vitro* against CQ-resistant and multi-resistant *P. falciparum* [8-9],
- *active in vivo* against CQ-resistant *P. falciparum* in the squirrel monkey model of human infection with CQ-resistant *P. falciparum* (enclosed Figures 1 and 2 in the Appendix), and
- *safe in human subjects* based on Phase 1 studies recently performed in New Orleans [11].

Therefore, we expect this Proof of Concept Study of AQ-13 in adults will demonstrate that AQ-13 is:

- *efficacious* for the treatment of human subjects with uncomplicated *P. falciparum* malaria – i.e., that the efficacy of AQ-13 will be similar to that of Coartem, and
- *safe* – i.e., that the adverse events (AEs) observed with AQ-13 will be similar to those of Coartem in these studies, as they were to CQ in the Phase 1 studies of AQ-13 and CQ [11].

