10 STATISTICAL CONSIDERATIONS

10.1 Study Outcome Measures

The primary, secondary and tertiary objectives (Section 3, above) and outcome measures (Section 8, above) in this study will be assessed statistically as outlined below (Table 7).

Table 7.

Statistical Assessment of Study Endpoints

COMPONENTS OF THE PRIMARY ENDPOINT

- Lack of recrudescence at 42 days
- < 25% of baseline asexual parasitemia on day 3
- Clearance of asexual parasitemia and fever by day 7

STATISTICAL TESTS

- Pearson χ^2 , Fisher Exact test
- Pearson χ^2 , Fisher Exact test
- Pearson χ^2 , Fisher Exact test

SECONDARY ENDPOINTS

- Adverse Events (AEs) Pearson χ^2 , Fisher Exact test
- Effects on the QT (QTc) Interval (within individuals) Wilcoxon, Friedman test
- Effects on the QT (QTc) Interval (between groups) ANOVA, Kruskal-Wallis test
- Pharmacokinetic Parameters for Parent Compounds (AUC_t, t_{1/2}, Vd/F, Cl/F, MRT) Mann-Whitney, Kruskal-Wallis
- Time to parasite Clearance, Recrudescence or Reinfection (between groups) Kaplan-Meier, Cox Hazard
- Time to fever clearance (between groups) Kaplan-Meier, Cox Hazard

TERTIARY ENDPOINTS

- Pharmacokinetics of metabolites as above
- Aminoquinoline (chloroquine) pruritus Fisher Exact test

AUC_t = total area under the curve; t_{1/2} = elimination half-life; Cl/F = oral clearance; Vd/F = oral apparent volume of distribution; MRT = mean residence time.

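### Section 10.3 tests non-inferiority at one-sided 0.025 without naming an interval method; at 26 to 33 men per arm that choice can decide the verdict, and a simple (Wald) interval would run at 4–5% error

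*Combined protocol and SAP*

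**What the plan says.** Section 10.3 sets H0 as C − E ≥ M and H1 as C − E < M, where C is the Coartem cure rate, E the AQ-13 cure rate and M = 15%. AQ-13 is accepted "if the null hypothesis is rejected with a one-sided alpha of 0.025". In practice, "differences between cure rates with AQ-13 and Coartem will be calculated with 95% confidence intervals", and non-inferiority is established if the upper limit "is less than the non-inferiority margin of 15" percent. References are cited for the rule, but the text names no interval (Wald, score, Newcombe or exact) and no test statistic.

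Section 10.1 says that the objectives and outcome measures "in this study will be assessed statistically as outlined below (Table 7"). Under the primary endpoint, Table 7 lists Pearson chi-square and Fisher exact tests for three components: recrudescence by day 42, parasitaemia on day 3, and clearance of parasites and fever by day 7. Composite cure, which is the primary outcome in Section 7.1.1, has no row.

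Section 10.2 plans on "an expected efficacy (cure rate) of 95% for Coartem" and "a conservative 20% estimate of attrition after treatment". It takes 33 per group at 80% power from Table 8.

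**The concern.** At 95% cure the expected number of failures per arm is 26 × 0.05 = 1.3, 28 × 0.05 = 1.4 or 33 × 0.05 = 1.65. With so few failures, the common intervals for a difference of two proportions do not agree, and the simplest one is too short. A rule stated only as a 95% confidence interval therefore leaves room for procedures with clearly different error rates. If the choice is made after the data are in, it can settle the only primary claim. Table 7 does not close the gap: in their usual form, chi-square and Fisher tests address equality, not H0: C − E ≥ 15%.

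**Working it through.** **Inputs.** Margin 15 points, one-sided 0.025 and the upper limit of a two-sided 95% interval (10.3). Coartem cure 95%, 80% power, 20% attrition and 33 per group (10.2). Evaluable per arm: 26 in the text after Table 8, 28 in Section 5.1. Assumption: AQ-13 cure for power equals Coartem's. No figure is given, only the expectation "that the efficacy of AQ-13 will be similar to that of Coartem", but equality reproduces Table 8.

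**Step 1: reproduce Table 8.** The unpooled normal formula is n = 2 × 0.95 × 0.05 × (z_α + z_0.80)² / 0.15², divided by (1 − dropout).

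| One-sided α | 0% dropout | 10% | 20% |
|---|---|---|---|
| 0.05 | 26.1 | 29.0 | 32.6 |
| 0.025 | 33.1 | 36.8 | 41.4 |
| Table 8, 15% margin | 26 | 29 | 33 |

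Table 8 matches the simple formula, but only at one-sided 0.05, not at the 0.025 of Section 10.3.

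**Step 2: two outcomes at 28 per arm.** Let p_E and p_C be the failure proportions for AQ-13 and Coartem, so that p_E − p_C equals C − E in cure.

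- Wald upper limit: (p_E − p_C) + 1.96 × √[p_E(1 − p_E)/n + p_C(1 − p_C)/n].
- Newcombe upper limit: (p_E − p_C) + √[(u_E − p_E)² + (p_C − l_C)²], where u_E and l_C are Wilson limits.

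AQ-13 1 failure, Coartem 0: Wald 0.0357 + 1.96 × √(0.0357 × 0.9643/28) = 0.0357 + 1.96 × 0.0351 = 10.4%, a pass. Newcombe 17.7%, a fail.

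Two failures in each arm: Wald 0 + 1.96 × √(2 × 0.0714 × 0.9286/28) = 1.96 × 0.0688 = 13.5%, a pass. Newcombe 16.3%, a fail.

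The Miettinen–Nurminen score interval also fails both. With no failures in either arm, the Wald interval has zero width.

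**Step 3: error and power by full enumeration.** For every pair of failure counts, apply the rule (upper limit below 0.15), then sum the binomial probabilities of the pairs that pass. Error is evaluated at Coartem 95% and AQ-13 80%; power at 95% in both arms.

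| Per arm | Error, Wald | Error, score or Newcombe | Power, Wald | Power, score or Newcombe | Opposite verdicts at 95%/95% |
|---|---|---|---|---|---|
| 26 | 5.1% | 2.0% | 72% | 43% | 28% |
| 28 | 4.0% | 2.1% | 70% | 55% | 15% |
| 33 | 4.2% | 2.2% | 81% | 59% | 22% |

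The last column is the Wald power minus the score power, apart from rounding, because in the outcomes that matter every score pass is also a Wald pass.

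**Step 4: sensitivity to the Coartem rate.** Section 10.2 cites cure rates from 93.9% to 97.5%. Over that range, with AQ-13 15 points lower, the Wald error is 4.8–5.8% at 26, 3.8–4.5% at 28 and 3.9–6.0% at 33. At 97%, the Wald figures are 5.6%, 4.3% and 5.5%, against 1.6%, 2.1% and 1.9% for score or Newcombe.

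**The case against.** No passage says that a Wald interval will be used. Table 8 is a planning table taken from a published source, and a planning formula does not fix the analysis interval. Since Table 8 matches only at one-sided 0.05, it is weak evidence of how the 95% interval of Section 10.3 would be built. The references cited there might specify a method; they cannot be checked here. All of this stands. A reader might infer that the promised 2.5% is not delivered, but the documents do not support that: a score interval fits the same text and holds about 2%.

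Table 7 labels its rows as components, and Section 7.2.1 separately plans to compare parasitologic outcomes between arms. Difference tests suit that purpose. Section 10.3 keeps hypotheses, margin and decision rule for the cure rate. So a reader might infer that Table 7 replaces the non-inferiority analysis, or that a non-significant test would be taken as proof of similarity. The plan does not say so: Section 10.3 ties similarity to the 15% margin. What remains is a missing row and an unstated status for the component tests.

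It can also be said that this is a proof-of-concept study. That lowers the stakes, but the plan itself commits to 0.025.

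**Conclusion.** The concern holds in conditional form and should be fixed. The primary decision rule is incomplete because the interval is unnamed. If Wald were chosen, the error would be about 4–5% at the plan's own rates and sizes, up to twice the stated 2.5%; a score or Newcombe interval keeps it at 2.0–2.2%. The disagreement falls on outcomes the plan should expect: 28%, 15% and 22% of trials at 26, 28 and 33 per arm when the drugs are truly equal at 95%.

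These figures rest on independent binomial outcomes, equal arm sizes, a 95% Coartem cure rate and no missing outcomes among those analysed. They describe what the wording permits, not what the sponsor is known to intend.

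**What to change.** In Section 10.3, state that non-inferiority is judged on the two-sided 95% Miettinen–Nurminen score interval for Coartem minus AQ-13 composite cure, with success if the upper limit is below 15 points. Newcombe is an acceptable equivalent: it gives the same verdicts at all three sizes for up to 5 Coartem failures per arm. Stating the direction also settles the present wording, which describes the interval as between AQ-13 and Coartem while the hypotheses use C − E.

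In Table 7, add a row for composite cure with this interval. Label the component chi-square and Fisher tests as descriptive and not part of the non-inferiority conclusion.

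The edit is short, but it has a consequence that must be stated. Power at equal 95% cure becomes 43%, 55% and 59% at 26, 28 and 33 per arm, so the 80% in Section 10.2 cannot stand, and the alpha behind Table 8 should be reconciled with 0.025. For scale, about 49 evaluable men per arm would give 82.8% power with 2.4% error, or 49/0.8 = 61.25, that is 62 per arm, before 20% attrition. If the sample size stays, the lower power should be reported openly. The method should be fixed before outcomes by arm are seen.
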